## 9.0 Ancillary Treatment/Supportive Care

### 9.1 Full Supportive Care

Patients should receive full supportive care while on this study. This includes blood product support, antibiotic treatment, and treatment of other newly diagnosed or concurrent medical conditions. All blood products and concomitant medications such as antidiarrheals, analgesics, and/or antiemetics received from within 28 days before the study treatment administration until 30 days after the final dose will be recorded in the medical records. **Leukocyte reduction of all blood products for patients on protocol is required. Any blood transfusions administered must be irradiated blood products to reduce the risk of transfusion mediated graft versus host disease in patients receiving T-cell modulating therapy.**

#### 9.11 Antiemetics

Antiemetics may be used at the discretion of the treating physician.

#### 9.12 NSAIDS

NSAIDs use limited to standard non-prescription doses.

#### 9.13 Blood Products and Growth Factors

Blood products and growth factors should be utilized as clinically warranted and following institutional policies and recommendations. The use of growth factors should follow published guidelines of the American Society of Clinical Oncology; Update of Recommendations for the Use of Hematopoietic Colony-Stimulating Factors: Evidence- Based, Clinical Practice Guidelines. J Clin Oncol 24(19): 3187-3205, 2006.

### 9.2 Suggested supportive care measures for the management of adverse events with potential immunologic etiology

Subjects should receive appropriate supportive care measures as deemed necessary by the treating investigator. Suggested supportive care measures for the management of adverse events with potential immunologic etiology are outlined below. Where appropriate, these guidelines include the use of oral or intravenous treatment with corticosteroids as well as additional anti-inflammatory agents if symptoms do not improve with administration of corticosteroids. Note that several courses of steroid tapering may be necessary as symptoms may worsen when the steroid dose is decreased. For each disorder, attempts should be made to rule out other causes such as metastatic disease or bacterial or viral infection, which might require additional supportive care. The treatment guidelines are intended to be applied when the investigator determines the events to be related to pembrolizumab.

Note: if after the evaluation the event is determined not to be related, the investigator does not need to follow the treatment guidance (as outlined below). Refer to Section 8.0 for dose modification.

It may be necessary to perform conditional procedures such as bronchoscopy, endoscopy, or skin photography as part of evaluation of the event.

- **Pneumonitis:**

- For **Grade 2 events**, treat with systemic corticosteroids. When symptoms improve to Grade 1 or less, steroid taper should be started and continued over no less than 4 weeks.
- For **Grade 3-4 events**, immediately treat with intravenous steroids. Administer additional anti-inflammatory measures, as needed.
- Add prophylactic antibiotics for opportunistic infections in the case of prolonged steroid administration.
- **Diarrhea/Colitis:**

Subjects should be carefully monitored for signs and symptoms of enterocolitis (such as diarrhea, abdominal pain, blood or mucus in stool, with or without fever) and of bowel perforation (such as peritoneal signs and ileus).

  - All subjects who experience diarrhea/colitis should be advised to drink liberal quantities of clear fluids. If sufficient oral fluid intake is not feasible, fluid and electrolytes should be substituted via IV infusion. For Grade 2 or higher diarrhea, consider GI consultation and endoscopy to confirm or rule out colitis.
  - For **Grade 2 diarrhea/colitis**, administer oral corticosteroids.
  - For **Grade 3 or 4 diarrhea/colitis**, treat with intravenous steroids followed by high dose oral steroids.
  - When symptoms improve to Grade 1 or less, steroid taper should be started and continued over no less than 4 weeks.
- **Type 1 diabetes mellitus (if new onset, including diabetic ketoacidosis [DKA]) or  $\geq$ Grade 3 Hyperglycemia, if associated with ketosis (ketonuria) or metabolic acidosis (DKA)**
  - For **T1DM or Grade 3-4 Hyperglycemia**
    - Insulin replacement therapy is recommended for Type I diabetes mellitus and for Grade 3-4 hyperglycemia associated with metabolic acidosis or ketonuria.
    - Evaluate patients with serum glucose and a metabolic panel, urine ketones, glycosylated hemoglobin, and C-peptide.
- **Hypophysitis:**
  - For **Grade 2 events**, treat with corticosteroids. When symptoms improve to Grade 1 or less, steroid taper should be started and continued over no less than 4 weeks. Replacement of appropriate hormones may be required as the steroid dose is tapered.
  - For **Grade 3-4 events**, treat with an initial dose of IV corticosteroids followed by oral corticosteroids. When symptoms improve to Grade 1 or less, steroid taper should be started and continued over no less than 4 weeks. Replacement of appropriate hormones may be required as the steroid dose is tapered.
- **Hyperthyroidism or Hypothyroidism:**

Thyroid disorders can occur at any time during treatment. Monitor patients for changes in thyroid function (at the start of treatment, periodically during treatment, and as indicated based on clinical evaluation) and for clinical signs

and symptoms of thyroid disorders.

- **Grade 2** hyperthyroidism events (and **Grade 2-4** hypothyroidism):
  - In hyperthyroidism, non-selective beta-blockers (e.g. propranolol) are suggested as initial therapy.
  - In hypothyroidism, thyroid hormone replacement therapy, with levothyroxine or liothyronine, is indicated per standard of care.
- **Grade 3-4** hyperthyroidism
  - Treat with an initial dose of IV corticosteroid followed by oral corticosteroids. When symptoms improve to Grade 1 or less, steroid taper should be started and continued over no less than 4 weeks. Replacement of appropriate hormones may be required as the steroid dose is tapered.
- **Hepatic:**
  - For **Grade 2** events, monitor liver function tests more frequently until returned to baseline values (consider weekly).
    - Treat with IV or oral corticosteroids
  - For **Grade 3-4** events, treat with intravenous corticosteroids for 24 to 48 hours.
  - When symptoms improve to Grade 1 or less, a steroid taper should be started and continued over no less than 4 weeks.
- **Renal Failure or Nephritis:**
  - For **Grade 2** events, treat with corticosteroids.
  - For **Grade 3-4** events, treat with systemic corticosteroids.
  - When symptoms improve to Grade 1 or less, steroid taper should be started and continued over no less than 4 weeks.
- **Management of Infusion Reactions:**  
 Signs and symptoms usually develop during or shortly after drug infusion and generally resolve completely within 24 hours of completion of infusion. Table 9.51 below shows treatment guidelines for subjects who experience an infusion reaction associated with administration of pembrolizumab.

Table 9.21 Infusion Reaction Treatment Guidelines

NCI CTCAE Grade	Treatment	Premedication at subsequent dosing
Grade 1 Mild reaction; infusion interruption not indicated; intervention not indicated	Increase monitoring of vital signs as medically indicated until the subject is deemed medically stable in the opinion of the investigator.	None
Grade 2 Requires infusion interruption but responds promptly to symptomatic treatment (e.g., antihistamines, NSAIDS,	Stop Infusion and monitor symptoms. Additional appropriate medical therapy may include but is not limited to: IV fluids Antihistamines	Subject may be premedicated 1.5h ( $\pm$ 30 minutes) prior to infusion of pembrolizumab with:  Diphenhydramine 50 mg po

NCI CTCAE Grade	Treatment	Premedication at subsequent dosing
narcotics, IV fluids); prophylactic medications indicated for < =24 hrs	NSAIDS Acetaminophen Narcotics Increase monitoring of vital signs as medically indicated until the subject is deemed medically stable in the opinion of the investigator. If symptoms resolve within one hour of stopping drug infusion, the infusion may be restarted at 50% of the original infusion rate (e.g., from 100 mL/hr to 50 mL/hr). Otherwise dosing will be held until symptoms resolve and the subject should be premedicated for the next scheduled dose. Subjects who develop Grade 2 toxicity despite adequate premedication should be permanently discontinued from further trial treatment administration.	(or equivalent dose of antihistamine) Acetaminophen 500-1000 mg po (or equivalent dose of antipyretic)
Grades 3 or 4 Grade 3: Prolonged (i.e., not rapidly responsive to symptomatic medication and/or brief interruption of infusion); recurrence of symptoms following initial improvement; hospitalization indicated for other clinical sequelae (e.g., renal impairment, pulmonary infiltrates) Grade 4: Life-threatening; pressor or ventilatory support indicated	Stop Infusion. Additional appropriate medical therapy may include but is not limited to: IV fluids Antihistamines NSAIDS Acetaminophen Narcotics Oxygen Pressors Corticosteroids Epinephrine Increase monitoring of vital signs as medically indicated until the subject is deemed medically stable in the opinion of the investigator. Hospitalization may be indicated. Subject is permanently discontinued from further trial treatment administration.	No subsequent dosing
Appropriate resuscitation equipment should be available in the room and a physician readily available during the period of drug administration.		

### 9.3 Diet/Activity/Other Considerations

#### 9.31 Diet

Subjects should maintain a normal diet unless modifications are required

to manage an AE such as diarrhea, nausea or vomiting.

### 9.32 Contraception

Pembrolizumab may have adverse effects on a fetus in utero. Furthermore, it is not known if pembrolizumab has transient adverse effects on the composition of sperm.

For this trial, male subjects will be considered to be of non-reproductive potential if they have azoospermia (whether due to having had a vasectomy or due to an underlying medical condition).

Female subjects will be considered of non-reproductive potential if they are either:

- (1) postmenopausal (defined as at least 12 months with no menses without an alternative medical cause; in women < 45 years of age a high follicle stimulating hormone (FSH) level in the postmenopausal range may be used to confirm a post-menopausal state in women not using hormonal contraception or hormonal replacement therapy. In the absence of 12 months of amenorrhea, a single FSH measurement is insufficient.);  
OR
- (2) have had a hysterectomy and/or bilateral oophorectomy, bilateral salpingectomy or bilateral tubal ligation/occlusion, at least 6 weeks prior to screening;  
OR
- (3) has a congenital or acquired condition that prevents childbearing.

Female and male subjects of reproductive potential must agree to avoid becoming pregnant or impregnating a partner, respectively, while receiving study drug and for 120 days after the last dose of study drug by complying with one of the following:

- (1) practice abstinence† from heterosexual activity;  
OR
- (2) use (or have their partner use) acceptable contraception during heterosexual activity.

Acceptable methods of contraception are‡:

Single method (one of the following is acceptable):

- intrauterine device (IUD)
- vasectomy of a female subject's male partner
- contraceptive rod implanted into the skin

Combination method (requires use of two of the following):

- diaphragm with spermicide (cannot be used in conjunction with cervical cap/spermicide)
- cervical cap with spermicide (nulliparous women only)
- contraceptive sponge (nulliparous women only)
- male condom or female condom (cannot be used together)
- hormonal contraceptive: oral contraceptive pill (estrogen/progestin pill or progestin-only pill), contraceptive skin patch, vaginal contraceptive ring, or subcutaneous

### contraceptive injection

†Abstinence (relative to heterosexual activity) can be used as the sole method of contraception if it is consistently employed as the subject's preferred and usual lifestyle and if considered acceptable by local regulatory agencies and ERCs/IRBs. Periodic abstinence (e.g., calendar, ovulation, sympto-thermal, post-ovulation methods, etc.) and withdrawal are not acceptable methods of contraception.

‡If a contraceptive method listed above is restricted by local regulations/guidelines, then it does not qualify as an acceptable method of contraception for subjects participating at sites in this country/region.

Subjects should be informed that taking the study medication may involve unknown risks to the fetus (unborn baby) if pregnancy were to occur during the study. In order to participate in the study subjects of childbearing potential must adhere to the contraception requirement (described above) from the day of study medication initiation (or 14 days prior to the initiation of study medication for oral contraception) throughout the study period up to 120 days after the last dose of trial therapy. If there is any question that a subject of childbearing potential will not reliably comply with the requirements for contraception, that subject should not be entered into the study.

#### 9.33 Use in Pregnancy

If a subject inadvertently becomes pregnant while on treatment with pembrolizumab, the subject will immediately be removed from the study. The site will contact the subject at least monthly and document the subject's status until the pregnancy has been completed or terminated. The outcome of the pregnancy will be reported to the Sponsor and to Merck without delay and within 24 hours to the Sponsor and within 2 working days to Merck if the outcome is a serious adverse experience (e.g., death, abortion, congenital anomaly, or other disabling or life-threatening complication to the mother or newborn).

The study investigator will make every effort to obtain permission to follow the outcome of the pregnancy and report the condition of the fetus or newborn to the Sponsor. If a male subject impregnates his female partner the study personnel at the site must be informed immediately and the pregnancy reported to the Sponsor and to Merck and followed as described above.

#### 9.34 Use in Nursing Women

It is unknown whether pembrolizumab is excreted in human milk. Since many drugs are excreted in human milk, and because of the potential for serious adverse reactions in the nursing infant, subjects who are breast-feeding are not eligible for enrollment.

[figure not shown]
**10.0 Adverse Event (AE) Reporting and Monitoring**

The site principal investigator is responsible for reporting any/all serious adverse events to the sponsor as described within the protocol, regardless of attribution to study agent or treatment procedure.

The sponsor/sponsor-investigator is responsible for notifying FDA and all participating investigators in a written safety report of any of the following:

- Any suspected adverse reaction that is both serious and unexpected.
- Any findings from laboratory animal or *in vitro* testing that suggest a significant risk for human subjects, including reports of mutagenicity, teratogenicity, or carcinogenicity.
- Any findings from epidemiological studies, pooled analysis of multiple studies, or clinical studies, whether or not conducted under an IND and whether or not conducted by the sponsor, that suggest a significant risk in humans exposed to the drug
- Any clinically important increase in the rate of a serious suspected adverse reaction over the rate stated in the protocol or Investigator’s Brochure (IB).

Summary of SAE Reporting for this study  
(please read entire section for specific instructions):

WHO:	WHAT form:	WHERE to send:
All sites	Pregnancy Reporting 	Mayo Sites – attach to MCCC Electronic SAE Reporting Form Non Mayo sites – complete and forward to 
Mayo Clinic Sites	Mayo Clinic Cancer Center SAE Reporting Form 	Will automatically be sent to 

Definitions

*Adverse Event*

Any untoward medical occurrence associated with the use of a drug in humans, whether or not considered drug related.

*Suspected Adverse Reaction*

Any adverse event for which there is a reasonable possibility that the drug caused the adverse event.

*Expedited Reporting*

Events reported to sponsor within 24 hours, 5 days or 10 days of study team becoming aware of the event.

*Routine Reporting*

Events reported to sponsor via case report forms

*Events of Interest*

Events that would not typically be considered to meet the criteria for expedited reporting, but that for a specific protocol are being reported via expedited means in order to facilitate the review of safety data (may be requested by the FDA or the sponsor).

*Unanticipated Adverse Device Event (UADE)*

Any serious adverse effect on health or safety or any life-threatening problem or death caused by, or associated with, a device, if that effect, problem, or death was not previously identified in nature, severity, or degree of incidence in the investigational plan or application (including a supplementary plan or application), or any other unanticipated serious problem associated with a device that relates to the rights, safety, or welfare of subjects

## 10.1 Adverse Event Characteristics

**CTCAE term (AE description) and grade:** The descriptions and grading scales found in the revised NCI Common Terminology Criteria for Adverse Events (CTCAE) version 4.0 will be utilized for AE reporting. All appropriate treatment areas should have access to a copy of the CTCAE version 4.0. A copy of the CTCAE version 4.0 can be downloaded from the CTEP web site:

- a. Identify the grade and severity of the event using the CTCAE version 4.0.
- b. Determine whether the event is expected or unexpected (see Section 10.2).
- c. Determine if the adverse event is related to the study intervention (agent, treatment or procedure) (see Section 10.3).
- d. Determine whether the event must be reported as an expedited report. If yes, determine the timeframe/mechanism (see Section 10.4).
- e. Determine if other reporting is required (see Section 10.5).
- f. Note: All AEs reported via expedited mechanisms must also be reported via the routine data reporting mechanisms defined by the protocol (see Sections 10.6 and 18.0).

NOTE: A severe AE is NOT the same as a serious AE, which is defined in Section 10.4.

## 10.2 Expected vs. Unexpected Events

*Expected events* - are those described within the Section 15.0 of the protocol, the study specific consent form, package insert (if applicable), and/or the investigator brochure, (if an investigator brochure is not required, otherwise described in the general investigational plan).

*Unexpected adverse events* or suspected adverse reactions are those not listed in Section 15.0 of the protocol, the study specific consent form, package insert (if applicable), or in the investigator brochure (or are not listed at the specificity or severity that has been observed); if an investigator brochure is not required or

available, is not consistent with the risk information described in the general investigational plan.

*Unexpected* also refers to adverse events or suspected adverse reactions that are mentioned in the investigator brochure as occurring with a class of drugs but have not been observed with the drug under investigation.

An investigational agent/intervention might exacerbate the expected AEs associated with a commercial agent. Therefore, if an expected AE (for the commercial agent) occurs with a higher degree of severity or specificity, expedited reporting is required.

NOTE: \*The consent form may contain study specific information at the discretion of the Principal Investigator; it is possible that this information may NOT be included in the protocol or the investigator brochure. Refer to protocol or IB for reporting needs.

### 10.3 Attribution to agent(s) or procedure

When assessing whether an adverse event (AE) is related to a medical agent(s) medical or procedure, the following attribution categories are utilized:

- Definite - The AE *is clearly related* to the agent(s)/procedure.
- Probable - The AE *is likely related* to the agent(s)/procedure.
- Possible - The AE *may be related* to the agent(s)/procedure.
- Unlikely - The AE *is doubtfully related* to the agent(s)/procedure.
- Unrelated - The AE *is clearly NOT related* to the agent(s)/procedure.

#### 10.31 EXPECTED Serious Adverse Events: Protocol Specific Exceptions to Expedited Reporting

For this protocol only, the following Adverse Events/Grades are expected to occur within this population and do not require Expedited Reporting. These events must still be reported via Routine Reporting (see Section 10.6).\*

\*Report any clinically important increase in the rate of a serious suspected adverse reaction (at your study site) over that which is listed in the protocol or investigator brochure as an expedited event.

\*Report an expected event that is greater in severity or specificity than expected as an expedited event.

CTCAE Category	Adverse Event	CTCAE Grade at which the event will not be reported in an expedited manner 
Blood and lymphatic system disorders	Anemia	≤Grade 4
Investigations	Platelet count decreased	≤Grade 4
	Neutrophil count decreased	≤Grade 4
	Lymphocyte count decreased	≤Grade 4
	White blood cell decreased	≤Grade 4

 These exceptions only apply if the adverse event does not result in hospitalization. If the adverse event results in hospitalization, then the standard expedited adverse events reporting requirements must be followed.

Specific protocol exceptions to expedited reporting should be reported expeditiously by investigators ONLY if they exceed the expected grade of the event.

The following hospitalizations are not considered to be SAEs because there is no “adverse event” (*i.e.*, there is no untoward medical occurrence) associated with the hospitalization:

- Hospitalizations for respite care
- Planned hospitalizations required by the protocol
- Hospitalization planned before informed consent (where the condition requiring the hospitalization has not changed post study drug administration)
- Hospitalization for elective procedures unrelated to the current disease and/or treatment on this trial
- Hospitalization for administration of study drug or insertion of access for administration of study drug
- Hospitalization for routine maintenance of a device (*e.g.*, battery replacement) that was in place before study entry
- Hospitalization, or other serious outcomes for signs and symptoms of progression of the cancer.]

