**10.4 Expedited Reporting Requirements for IND/IDE Agents**

10.41 Late Phase 2 and Phase 3 Studies: Expedited Reporting Requirements for Adverse Events that Occur on Studies under an IND/IDE within 30 Days of the Last Administration of the Investigational Agent/Intervention

FDA REPORTING REQUIREMENTS FOR SERIOUS ADVERSE EVENTS (21 CFR Part 312)				
NOTE: Investigators MUST immediately report to the sponsor ANY Serious Adverse Events, whether or not they are considered related to the investigational agent(s)/intervention (21 CFR 312.64)				
An adverse event is considered serious if it results in ANY of the following outcomes:				
1) Death				
2) A life-threatening adverse event				
3) An adverse event that results in inpatient hospitalization or prolongation of existing hospitalization for ≥ 24 hours				
4) A persistent or significant incapacity or substantial disruption of the ability to conduct normal life functions				
5) A congenital anomaly/birth defect.				
6) Important Medical Events (IME) that may not result in death, be life threatening, or require hospitalization may be considered serious when, based upon medical judgment, they may jeopardize the patient or subject and may require medical or surgical intervention to prevent one of the outcomes listed in this definition. (FDA, 21 CFR 312.32; ICH E2A and ICH E6).				
ALL SERIOUS adverse events that meet the above criteria MUST be immediately reported to the sponsor within the timeframes detailed in the table below.				
Hospitalization	Grade 1 Timeframes	Grade 2 Timeframes	Grade 3 Timeframes	Grade 4 & 5 Timeframes
Resulting in Hospitalization ≥24 hrs	7 Calendar Days			24-Hour 3 Calendar Days
Not resulting in Hospitalization ≥24 hrs	Not required		7 Calendar Days	

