#### 10.52 Death

**Note: A death on study requires both routine and expedited reporting regardless of causality, unless as noted below. Attribution to treatment or other cause must be provided.**

Any death occurring within 30 days of the last dose, regardless of attribution to an agent/intervention under an IND/IDE requires expedited reporting within 24-hours.

Any death occurring greater than 30 days with an attribution of possible, probable, or definite to an agent/intervention under an IND/IDE requires expedited reporting within 24-hours.

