10.84 Protocol-Specific Exceptions to Serious Adverse Event Reporting

Efficacy endpoints as outlined in this section will not be reported to Merck as described in Section 10.1.- Immediate Reporting of Adverse Events to the Sponsor and to Merck, unless there is evidence suggesting a causal relationship between the drug and the event. Any such event will be submitted to the Sponsor within 24 hours and to Merck Global Safety within 2 working days either by electronic or paper media.

Specifically, the suspected/actual events covered in this exception include any event that is disease progression of the cancer under study.

The Sponsor will monitor unblinded aggregated efficacy endpoint events and safety data to ensure the safety of the subjects in the trial. Any suspected endpoint which upon review is not progression of the cancer under study will be forwarded to Merck Global Safety as a SAE within 2 working days of determination that the event is not progression of the cancer under study

Hospitalization related to convenience (e.g. transportation issues etc.) will not be considered a SAE.

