## 11.0 Treatment Evaluation

**NOTE:** For assessment of index (target) and non-target lesions on whole body scan performed after completion of DC treatment, the baseline whole body scan will be used to assess overall treatment response of index (target) and non-target lesions. Include up to 6 index (target) lesions as measurable disease when assessing overall clinical response. The treatment lesion(s) is the lesion(s) that is cryoablated. This treatment lesion will be measured only at baseline and will not be included in assessment of overall clinical response, and will not be followed or measured.

**NOTE:** Subject(s) with progressive disease on anti-PD-1 monoclonal antibody alone prior to receiving cryoablation and intra-tumor injection of autologous DC will be continued on treatment to assess clinical response with the addition of these therapy as long as the provider and the investigator deemed clinically safe and reasonable.

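### The last bullet of 10.31 removes serious outcomes of progression from SAE status with no causality exception, in conflict with 10.84 and, if death is included, with 10.52

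*Combined protocol and SAP*

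**What the plan says.** Section 10.31 ends with a list introduced by "The following hospitalizations are not considered to be SAEs because there is no" adverse event behind the admission. Six of its seven bullets describe admissions such as respite care, planned stays or device maintenance. The seventh reads "Hospitalization, or other serious outcomes for signs and symptoms of progression of the cancer". It sets no attribution test and does not name death.

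Section 10.41 requires every SAE to go to the sponsor whether or not it is thought related, and puts death first among the serious outcomes. Its closing note sends the reader to 10.31 for exceptions.

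Section 10.52 opens with "A death on study requires both routine and expedited reporting regardless of causality, unless as noted below" and continues: "Any death occurring within 30 days of the last dose, regardless of attribution to an agent/intervention under an IND/IDE requires expedited reporting within 24-hours". Later deaths need a 24-hour report if at least possibly related. Death from progressive disease has its own Grade 5 reporting term, and supporting evidence is to be submitted.

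Section 10.84 leaves progression events out of reporting to the drug company "unless there is evidence suggesting a causal relationship between the drug and the event". Where such evidence exists, the event goes to the sponsor within 24 hours and to the drug company within 2 working days. It adds a second check: "Any suspected endpoint which upon review is not progression of the cancer under study will be forwarded to Merck Global Safety as a SAE". Section 10.8 also leaves death from progression out of its own 24-hour rule.

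**The concern.** The same event can fall under two instructions. A life-threatening event that the investigator labels progression, but with some evidence pointing to the drug, is a 24-hour report under 10.84. Under 10.31 it is not an SAE. Because 10.41 yields to 10.31, a site that follows the cross-reference can file no expedited report and believe it has complied.

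The label can arise while patients are still receiving study treatment. Section 11.0 says "Subject(s) with progressive disease on anti-PD-1 monoclonal antibody alone prior to receiving cryoablation and intra-tumor injection of autologous DC will be continued on treatment", provided this is judged safe and reasonable. Such a patient already has progression on record when a later serious event has to be classified. At stake is how soon the sponsor learns of a possibly treatment-related serious event in a trial of a combination whose safety is a stated objective (2.223).

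**Working it through.** No arithmetic applies. The check is to put each type of event through each section.

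| Event labelled progression | 10.31, last bullet | 10.52 | 10.84 | Result |
|---|---|---|---|---|
| Hospitalization, no evidence of a drug link | Not an SAE | Not applicable | Exempt | Consistent |
| Non-fatal serious outcome, evidence of a drug link | Not an SAE | Not applicable | Sponsor in 24 hours, drug company in 2 working days | Conflict |
| Death within 30 days of last dose, no evidence of a drug link | Not an SAE if death is covered; silent if not | 24-hour report | Exempt from drug-company reporting | Conflict with 10.52 on the wide reading only |
| Death after 30 days, at least possibly related | As above | 24-hour report | Sponsor in 24 hours if the evidence points to the drug | Conflict on the wide reading only |
| Death after 30 days, unlikely or unrelated | As above | No 24-hour rule applies | Exempt | Consistent |

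Three points follow.

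1. The second row does not depend on how death is read. A hospitalization or life-threatening event is enough, and the missing causality exception alone produces the conflict.
2. The conflict with 10.52 depends on whether other serious outcomes include death. In favour: 10.41 puts death first among serious outcomes, and nothing in the bullet excludes it. Against: the lead-in speaks only of hospitalizations, and 10.52 is the specific rule for deaths.
3. Sections 10.8 and 10.52 can stand together, because 10.8 sets additional instructions and does not cancel 10.52. They should still be read against each other when 10.31 is amended.

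The other routes to the sponsor are these. Section 10.62 asks for Grade 3 and 4 AEs, and any death within 30 days, on case report forms regardless of attribution. Section 10.0 defines routine reporting as reporting to the sponsor through those forms. Section 16.53 promises a review of grade 4 and 5 events judged unrelated or unlikely. Both routes limit the loss but do not remove it. A case report form does not meet a 24-hour duty. The 10.31 list also rests on there being no adverse event at all, and the sentence in 10.31 that preserves routine reporting stands over the table of blood-count exceptions and is not repeated for this list.

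**The case against.** The strongest reply is that this is loose wording inside a system with several safeguards. Deaths have their own rule in 10.52. Severe events reach the sponsor through 10.62 whatever their attribution. Section 16.53 rechecks grade 4 and 5 attributions, 16.51 adds weekly monitoring, 16.52 adds board review at least twice a year, and 18.5 requires imaging reports for progression. Moreover, 10.84 and 10.8 themselves exempt progression by default, so on the ordinary case they agree with 10.31. Finally, the bullet covers only signs and symptoms of progression, and an event caused by treatment is not one.

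Most of this stands, and it limits the point to expedited reporting. The last argument does not dispose of it. Section 10.84 exists because an event classed as progression may still show evidence of a drug cause, and it says what to do then; 10.31 does not.

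A reader might infer more than the documents support:

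- That such events never reach the sponsor. Sections 10.52, 10.62, 10.84 and 16.53 leave several routes open.
- That the exemption could cover most serious outcomes. At the plan's two response rates (16.31), non-responders among 28 patients would number 28 × (1 − 0.53) = 13.2 to 28 × (1 − 0.30) = 19.6. That group includes stable disease and patients with no serious event, so it is not an event count.
- That the safety objective is biased. Section 16.325 tabulates the maximum grade of each adverse event type and does not count SAEs.
- That the documents show treatment reactions being mistaken for symptoms of progression. The nearest text is the new-lesion row of the PET criteria in 11.2, which names infection and inflammation as other causes of uptake on a scan.

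**Conclusion.** The point holds as a conflict between reporting rules and is worth correcting. The bullet is wider than its lead-in and lacks the causality exception that 10.84 carries. For a non-fatal serious event labelled progression with evidence of a drug link, the conflict with 10.84 is direct. For a death within 30 days of the last dose, the conflict with 10.52 exists only if the bullet is taken to include death, which the text neither says nor rules out.

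The consequence is possible omission or delay of an expedited report, mainly for non-fatal events. Its frequency cannot be given, because the documents state no rate of serious outcomes and none of mislabelling. The conclusion assumes that a site applies 10.31 as the exception that 10.41 says it is. The separate exclusion of progression-related deaths from the 16.53 accrual pause is a different provision, which correcting 10.31 would not alter.

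**What to change.** Amend the last bullet of 10.31 and reconcile it with 10.52, 10.8 and 10.84:

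- Strike the words that extend the bullet from hospitalization to other serious outcomes.
- Limit it to hospitalization for progression where no evidence suggests a causal relationship to study treatment. Section 10.84 speaks only of the drug; naming study treatment also covers the dendritic cells, the cryoablation and the pneumococcal vaccine.
- State that all deaths are handled under 10.52.

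While 10.8 is open, correct its pointer to a Section 10.10.1, which the protocol does not contain.

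The cost is a short text amendment and a few more expedited reports. No added patients, tests or data items are needed.
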